5.4 Safety Analysis

All safety parameters will be summarized descriptively by treatment group for the entire study period.

Study drug duration and SoC therapies will be described for each treatment group.

All reported AEs will be coded into preferred term (PT) and grouped by SOC using the most recent Medical Dictionary for Regulatory Activities version. An overall summary will be provided with the number and percentage of patients reporting TEAEs, serious TEAEs,

This document is confidential.

Page 73 of 85

MP1032-CT05 Protocol v2.0

treatment-related TEAEs, TEAEs leading to withdrawal, and TEAEs leading to death. For patients with any serious TEAE and for patients with any related serious TEAE exposureadjusted events rates will be calculated and compared between treatment groups using the risk ratio [(300 mg MP1032 BID plus SoC) / (placebo plus SoC)] with respective 95% confidence intervals. This comparison will also be performed for the rate of rehospitalization which is considered a serious AE. The number and percentage of patients with TEAEs, serious TEAEs, TEAEs leading to withdrawal, and treatment-related TEAEs will be summarized by SOC and PT for each treatment group, and total. In these tables, the incidence of TEAEs by SOC and PT will also be included. TEAEs will also be summarized by maximum severity and relationship to study drug. Events with missing onset dates will be considered as TEAEs. If a patient experienced >1 occurrence of the same AE, the occurrence with the greatest severity and the closest association with the study drug will be used in the corresponding summary tables. In case that for one AE several AE episodes with changing severity is reported, an aggregation of all respective episodes to one AE will be performed before summarization. The worst severity and the worst causality will be assigned to the aggregated AE and used for the respective AE summaries. All reported AE episodes will be listed by patient, along with information regarding onset, duration, severity and relationship to study drug, action taken with study drug, treatment of event, and outcome. Additionally, the aggregated AEs with the resulting worst severity and worst relationship will be included in the AE listings.

Vital signs including SpO₂ (%) will be summarized using descriptive statistics, including mean values and mean change from baseline values. Clinical laboratory data of local laboratories will be presented with the number and percentage of patients with values below, within, or above the normal range at each time point. Additionally, a shift table of the number and percentage of patients with normal and abnormal, and clinically significant abnormal values at each scheduled postbaseline visit compared with the normal/abnormal/clinically significant abnormal categorization at baseline will be provided by treatment group. Summarizing of clinical laboratory data of local laboratories using descriptive statistics, including mean values and mean change from baseline values will be only possible after normalization of the values using a reference laboratory. Details for normalization will be provided in the SAP.

Summary tables will be provided for concomitant medications.

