12.6 Adverse Events

12.6.1 Adverse Events

An AE is any symptom, physical sign, syndrome, or disease that either emerges during the study or, if present at screening, worsens during the study, regardless of the suspected cause of the event. All medical and psychiatric conditions (except those related to the indication under study) present at screening will be documented on the medical history eCRF. Changes in these conditions and new symptoms, physical signs, syndromes, or diseases should be noted on the AE eCRF during the rest of the study. Clinically significant laboratory abnormalities should also be recorded as AEs. Surgical procedures that were planned before the patient was randomized in the study are not considered AEs if the conditions were known before study inclusion; the medical condition should be reported in the patient's medical history.

Patients will be instructed to report AEs at each study visit. All AEs are to be followed up until resolution or a stable clinical endpoint is reached.

Each AE is to be documented on the eCRF with reference to date of onset, duration, frequency, severity, relationship to study drug, action taken with study drug, treatment of event, and outcome. Furthermore, each AE is to be classified as being serious or nonserious. Changes in AEs and resolution dates are to be documented on the eCRF.

For the purposes of this study, the period of observation for collection of AEs extends from the time the patient gives informed consent until the end of the follow-up period (Day 60). Follow-up of the AE, even after the date of study completion, is required (if possible) if the AE persists. The follow-up should continue until the event resolves (returns to normal or baseline values) or stabilizes, or until it is judged by the investigator to no longer be clinically significant. It is understood that if a patient withdraws consent to further follow-up, then it may not be possible for the study site to follow the AE to resolution.

When changes in the severity of an AE occur more frequently than once a day, the maximum severity for the event should be noted. If the severity category changes over a number of days, then those changes should be recorded separately (with distinct onset dates).

This document is confidential.

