12.6.2 Serious Adverse Events

An SAE is any untoward medical occurrence, in the view of either the investigator or sponsor, that:

- results in death
- is life-threatening
- results in inpatient hospitalization or prolongation of existing hospitalization
- results in persistent or significant disability/incapacity
- is a congenital anomaly/birth defect

This document is confidential.

Page 64 of 85

MetrioPharm AG MP1032	MP1032-CT05	
	Final	
MetrioPharm AG	MP1032-CT05	
MP1032	Protocol v2.0	

Other important medical events that may not be immediately life-threatening or result in death or hospitalization, based upon appropriate medical judgment, are considered SAEs if they are thought to jeopardize the patient and/or require medical or surgical intervention to prevent 1 of the outcomes defining an SAE. SAEs are critically important for the identification of significant safety problems; therefore, it is important to take into account both the investigator's and the sponsor's assessment. If either the sponsor or the investigator believes that an event is serious, the event must be considered serious and evaluated by the sponsor for expedited reporting.

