12.6.3 Serious Adverse Event Reporting

An SAE occurring from the time the patient gives informed consent until the end of the followup period (Day 60) or within 30 days of stopping the study drug (whichever is longer) must be reported to the Syneos Health Safety and Pharmacovigilance group and will be communicated to the sponsor. Any such SAE due to any cause, whether or not related to the study drug, must be reported within 24 hours the investigator's awareness of the event. Notification can be made using the dedicated fax line or email for the Syneos Health Safety and Pharmacovigilance group:

- Syneos Health Safety and Pharmacovigilance fax number: CCI
- Syneos Health Safety and Pharmacovigilance email address:

If the investigator contacts the Syneos Health Safety and Pharmacovigilance group by telephone, then a written report must follow within 24 hours and has to include a full description of the event and sequelae in the format detailed in the SAE reporting form.

The event must also be recorded on the standard AE eCRF. Preliminary reports of SAEs must be followed up by detailed descriptions later on. Clear and anonymized photocopies of hospital case reports, consultant reports, autopsy reports, and other documents must be provided when requested by Syneos Health Safety and Pharmacovigilance. SAE reports must be made whether or not the investigator considers the event to be related to the investigational drug.

Appropriate remedial measures should be taken to treat the SAE, and the response should be recorded. Clinical, laboratory, and diagnostic measures should be employed as needed to determine the etiology of the problem. The investigator must report all additional follow-up evaluations to the Syneos Health Safety and Pharmacovigilance group within 24 hours of becoming aware of the additional information. All SAEs will be followed up until the investigator and sponsor agree the event is satisfactorily resolved.

Any SAE that is not resolved by the end of the study or upon discontinuation of the patient's participation in the study is to be followed up, if possible, until it either resolves, stabilizes, returns to baseline values (if a baseline value is available), or is shown to not be attributable to the study drug or procedures. It is understood that if a patient withdraws consent to further follow-up, then it may not be possible for the study site to follow the SAE to resolution.

This document is confidential.

Page 65 of 85

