15.8 Data Monitoring Committee

An independent DMC will be established by the sponsor or designee to review accumulating study data at regular intervals (as per the DMC charter) throughout the study to ensure the safety of patients and review overall study conduct. Additional data may be reviewed that are related to efficacy, but the DMC will only be reviewing data for risk-benefit purposes. Members will include experts in drug safety and/or medical specialist and biostatistics, who are not participating in this study and do not have affiliation with the investigators or the sponsor. The DMC can recommend in writing to the sponsor whether to continue, modify, or stop the clinical study on the basis of safety considerations. The pre-specified study stopping rules for the trial are defined as follows:

- death (not including disease progression) in any patient in whom the cause of death is judged to be related to the study drug by investigator
- the occurrence in any patient of a SAE whose causal relationship (ie, without a plausible alternative explanation) to the study drug is judged to be related by investigator
- two occurrences of a clinically significant Grade 3 or higher laboratory abnormality assessed to be related to the study drug by investigator.

The DMC's specific duties will be fully described in a DMC charter.

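### The planned serious-TEAE ratio does not separate COVID-19 progression from other harm, so it can fall below 1 while serious non-COVID harm doubles

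*Protocol*

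**What the plan says.** Section 15.4 (Safety Analysis) fixes a between-arm comparison in the protocol itself. It is planned "For patients with any serious TEAE and for patients with any related serious TEAE". The measure is an event rate adjusted for exposure, MP1032 divided by placebo, with 95% confidence intervals; the protocol calls it a risk ratio. The same comparison is planned for rehospitalization. Serious TEAEs are also tabulated by system organ class and preferred term, and all AE episodes are listed by patient.

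The definitions that feed this analysis are broad:

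- Section 12.6.1 counts as an AE a condition that emerges or, "if present at screening, worsens during the study, regardless of the suspected cause of the event".
- Section 12.6.2 makes an event serious if, among other criteria, it "results in death", is life-threatening, or "results in inpatient hospitalization or prolongation of existing hospitalization". Every patient is an inpatient at entry (Section 8.1).
- Section 12.6.3 sets the reporting scope: "Any such SAE due to any cause, whether or not related to the study drug, must be" reported.

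The one explicit exception for disease progression is a stopping rule in Section 15.8, which concerns "death (not including disease progression) in any patient" where the investigator judges the cause to be drug-related. Section 15.4 has no such exception.

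The primary endpoint (Section 6.2) is death or a NIAID score of 2, 3 or 4 at Day 14.

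**The concern.** A COVID-19 death, or a worsening to ventilation that is life-threatening or prolongs the stay, can be counted twice: once as a primary-endpoint failure and once in the any-serious-TEAE ratio. That ratio then answers two questions at once.

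If the drug reduces progression, fewer COVID-19 events on MP1032 pull the ratio down and can offset a rise in other serious harm. If the drug has no effect on progression, a large common background of COVID-19 events pulls the ratio towards 1 and dilutes the same rise. In either case a reader who takes the ratio as a measure of toxicity may be falsely reassured.

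**Working it through.** **Planning figure.** Section 15.1 assumes progression of 10% vs 30%, 76 vs 38 patients and two-sided alpha 10%, and states 83% power. Pooled proportion = (76×0.10 + 38×0.30)/114 = 0.1667. Null SE = √[0.1667×0.8333×(1/76 + 1/38)] = 0.0740. Alternative SE = √(0.09/76 + 0.21/38) = 0.0819. Power = Φ[(0.20 − 1.645×0.0740)/0.0819] = Φ(0.955) = 83.0%. The stated figure reproduces, so 10% vs 30% is used below.

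**Inputs**

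- p = 0.10 (MP1032) and 0.30 (placebo), from Section 15.1. Day 14 status stands in for the risk of progression.
- f = share of these progressions that are also SAEs. Not in the protocol; assumed 0.25 to 1.
- b = placebo risk of a serious event unrelated to COVID-19. Not in the protocol; assumed 2% to 20%. It is set to 2b on MP1032, a doubling.
- The two sources of events are taken as independent.

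**Formula.** P(any serious TEAE) = 1 − (1 − f·p)(1 − non-COVID risk).

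Example with b = 5%:

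- f = 1: MP1032 1 − 0.90×0.90 = 19.0%; placebo 1 − 0.70×0.95 = 33.5%; ratio 0.57.
- f = 0.5: MP1032 1 − 0.95×0.90 = 14.5%; placebo 1 − 0.85×0.95 = 19.3%; ratio 0.75.

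Ratios when non-COVID serious harm doubles:

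| f | b = 2% | b = 5% | b = 10% | b = 20% |
|---|---|---|---|---|
| 1 | 0.43 | 0.57 | 0.76 | 1.05 |
| 0.75 | 0.47 | 0.64 | 0.86 | 1.17 |
| 0.5 | 0.53 | 0.75 | 1.02 | 1.34 |
| 0.25 | 0.68 | 1.01 | 1.31 | 1.60 |

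**Break-even.** Setting (1 − 0.10f)(1 − 2b) = (1 − 0.30f)(1 − b) gives b = 0.20f/(1 + 0.10f):

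- f = 1: 0.20/1.10 = 18.2%
- f = 0.75: 0.15/1.075 = 14.0%
- f = 0.5: 0.10/1.05 = 9.5%
- f = 0.25: 0.05/1.025 = 4.9%

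Below these values of b the ratio is under 1 despite the doubling. With f = 1 and a smaller benefit, break-even falls to 11.1% (20% vs 30%) and 6.25% (25% vs 30%).

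**No benefit.** With 30% progression in both arms, f = 1 and b = 5%: (1 − 0.70×0.90)/(1 − 0.70×0.95) = 0.370/0.335 = 1.10, where the non-COVID ratio is 2.0.

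**Scale.** The plan uses exposure-adjusted rates. Under constant hazards and equal exposure the rate ratio is ln(1 − P_MP1032)/ln(1 − P_placebo). For f = 1 and b = 5% this is 0.52 against 0.57. On these assumptions the break-even points do not change, because equal risks mean equal rates. Exposure may not be equal, however. Section 9.4 requires study drug to stop at invasive ventilation, so if exposure means time on drug, an effective drug would leave placebo with less exposure and push the ratio lower still.

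**With progression separated.** At b = 5% and 80/40 patients, about 8 vs 2 patients have a non-COVID serious event. Ratio = 0.10/0.05 = 2.0. SE of the log ratio = √(1/8 − 1/80 + 1/2 − 1/40) = 0.766. The 95% CI is about 0.45 to 9.0.

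**The case against.** The strongest reply is that the safety analysis is descriptive and does not rest on this one ratio. Section 15.4 also plans a ratio for related serious TEAEs, a rehospitalization ratio, tables by system organ class and preferred term, and listings. The SAP, which is not shown, may add a cut without progression.

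Much of this stands, but it does not remove the problem. The related-serious ratio rests on investigator causality, and Table 7 directs events that the patient's clinical state could explain away from a drug attribution. The tables give counts by term but no pooled contrast with an interval. The rehospitalization ratio covers one event type and does not exclude COVID-19 readmissions. The comparison of any serious TEAE is written into the protocol without the separation.

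Four stronger readings are tempting, and the protocol does not support them:

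- *An effective drug always gets a ratio below 1.* It depends on f and b. At f = 0.25 and b = 5% a doubling gives 1.01. At f = 0.5 a tripling (15% vs 5%) gives 0.1925/0.1925 = 1.00.
- *Every primary-endpoint failure is a serious TEAE.* Score 4 is supplemental oxygen in hospital. An oxygen need unchanged since entry is not a worsening, so it is not automatically an AE.
- *COVID-19 worsening is unambiguously reportable.* Section 12.6.1 leaves indication-related conditions out of the medical history form and then sends changes in the documented conditions to the AE form. That sits uneasily with its own general AE definition.
- *The comparison without progression should replace the all-cause one.* Doing so could hide COVID-19 worsening caused by the drug. Section 5.3 itself flags a possible additive effect with dexamethasone on inflammation.

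**Conclusion.** The point holds in conditional form. Section 15.4 does not separate COVID-19 progression in the any-serious-TEAE ratio, so that ratio can fall below 1 while serious non-COVID harm doubles. At 10% vs 30% this happens when placebo non-COVID serious risk is below about 18%, 9.5% or 4.9%, for all, half or a quarter of progressions being SAEs. With no benefit, under the inputs shown, a doubling appears as about 1.10.

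These figures rest on assumed values of f and b, on independence of the two sources, and on simple cumulative risks instead of the planned exposure-adjusted rates. The primary efficacy analysis is not affected. What is affected is how far the all-cause safety ratio can be read as evidence about harm.

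**What to change.** In Section 15.4:

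1. Keep the all-cause serious-TEAE ratio.
2. Add alongside it the same comparison, with the same exposure adjustment and 95% interval, for serious TEAEs excluding COVID-19 progression and COVID-19 death. Define the excluded events by a preferred-term list fixed before unblinding, together with the cause-of-death field and its relatedness to COVID-19, which Section 11.3 and the Schedule of Assessments already collect.

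In Section 12.6.1, reconcile the wording on indication-related conditions with the general AE definition and with the stopping rule in Section 15.8, so that all sites report progression in the same way.

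The cost is protocol and SAP wording plus one blinded term list; no new data are needed. The drawback is few events and a wide interval, as in the 8/80 vs 2/40 example above, so the added ratio should be labelled descriptive.

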15.5 Pharmacokinetic Analysis

The PK parameters (such as C_{max}, T_{max}, AUC_{0-t}, and others) of MP1032 on Day 1 (single dose) and Day 7 (steady state; if available), using up to 8 hours postdose, will be derived applying noncompartmental analysis. PK parameters will be summarized along with plasma concentrations at various time points. Individual and mean plasma concentration versus time will be presented on linear, and semi-log scales. Further details of the PK analysis will be described in the SAP. Any possible correlation between plasma exposure and biomarkers (eg, change from baseline in cytokines, or other coagulation/inflammatory biomarkers) or efficacy measures can be explored by appropriate regression analysis methods during the final data analysis.

This document is confidential.

Page 74 of 85

MetrioPharm AG	MP1032-CT05
MP1032	Protocol v2.0

15.6 Biomarker Analysis

The change from baseline biomarker levels will be summarized descriptively by treatment group and visit. The change in biomarker levels will also be evaluated with any change of COVID-19 clinical status.

15.7 Interim Analysis

Not applicable.

15.8 Data Monitoring Committee

An independent DMC will be established by the sponsor or designee to review accumulating study data at regular intervals (as per the DMC charter) throughout the study to ensure the safety of patients and review overall study conduct. Additional data may be reviewed that are related to efficacy, but the DMC will only be reviewing data for risk-benefit purposes. Members will include experts in drug safety and/or medical specialist and biostatistics, who are not participating in this study and do not have affiliation with the investigators or the sponsor. The DMC can recommend in writing to the sponsor whether to continue, modify, or stop the clinical study on the basis of safety considerations. The pre-specified study stopping rules for the trial are defined as follows:

- death (not including disease progression) in any patient in whom the cause of death is judged to be related to the study drug by investigator
- the occurrence in any patient of a SAE whose causal relationship (ie, without a plausible alternative explanation) to the study drug is judged to be related by investigator
- two occurrences of a clinically significant Grade 3 or higher laboratory abnormality assessed to be related to the study drug by investigator.

The DMC's specific duties will be fully described in a DMC charter.

16 STUDY MANAGEMENT

161 Approval and Consent

16.1.1 Regulatory Guidelines

This study will be conducted in accordance with the accepted version of the Declaration of Helsinki and all relevant regulations as set forth in Parts 50, 56, 312, Subpart D, of Title 21 of the United States Code of Federal Regulations (CFR), in compliance with International Council for Harmonisation and GCP guidelines and according to the appropriate regulatory requirements in the countries where the study will be conducted.

This document is confidential.

Page 75 of 85

16.1.2 Institutional Review Board/Independent Ethics Committee

Conduct of the study must be approved by an appropriately constituted IRB/IEC. Approval is required for the study protocol, protocol amendments (if applicable), IB, ICFs, recruitment material and patient information sheets, and other patient-facing material.

16.1.3 Informed Consent

For each patient (or the patient's LAR), informed consent will be obtained before any protocol-related activities. As part of this procedure, the principal investigator (PI) or designee must explain the nature of the study, its purpose, procedures, expected duration, alternative therapy available, and the benefits and risks involved in study participation. The patient (or the patient's LAR) should be informed that he/she may withdraw from the study at any time, and the patient will receive all information that is required by local regulations and guidelines for International Council for Harmonisation. The PI will provide the sponsor or its representative with a copy of the IRB/IEC-approved ICF before the start of the study.

16.2 **Data Handling**

Data reported on the eCRF that are derived from source documents should be consistent with the source documents, or the discrepancies must be explained (see also Section 16.3).

Clinical data will be entered by site personnel on eCRFs for transmission to the sponsor. Data on eCRFs transmitted via the web-based data system must correspond to and be supported by source documentation maintained at the study site. All study forms and records transmitted to the sponsor must only include coded identifiers such that directly identifying personal information is not transmitted. The primary method of data transmittal is via the secure, internet-based electronic data capture (EDC) system maintained by Syneos Health. Access to the EDC system is available to only authorized users via the study's internet website, where a user unique assigned username and password are required for access.

Any changes made to data after collection will be made through the use of data clarification forms or the EDC system. When all missing and/or incorrect data have been resolved, eCRFs will be considered complete.

Source Documents 16.3

Source documents are considered to be all information in original records and certified copies of original records of clinical findings, observations, data, or other activities in a clinical study necessary for the reconstruction and evaluation of the study. The investigator will provide direct access to source documents and/or source data in the facilitation of study-related monitoring, audits, review by IRB/IECs, and regulatory inspections.

The investigator/institution should maintain adequate and accurate source documents and study records that include all pertinent observations on each of the site's patients. Source data should

This document is confidential.

Page 76 of 85

Final

MetrioPharm AG	MP1032-CT05	
MP1032	Final	
MetrioPharm AG	MP1032-CT05	
MP1032	Protocol v2.0	

be attributable, legible, contemporaneous, original, accurate, and complete. Changes to source data should be traceable, not obscure the original entry, and be explained if necessary.

